Dehydration is a complex condition resulting in a reduction in total body water (6), including water loss dehydration (due to water deficit, which can be hypernatraemic or hyponatraemic in the presence of hyperglycaemia) and salt loss dehydration (due to salt and water deficit, generally hyponatraemic, rarely isotonic). The reference standard for water loss dehydration is debated. While serum osmolality is a strong contender, disadvantages include slow response to dehydration and rehydration (14), but these are outweighed by its advantages. Advantages include that it can be measured at a single assessment (change in weight over a short period signals change in hydration but requires assessment over several days), is associated with health outcomes, and directly measures amounts of effective solute in plasma - as these solutes are impermeable to cell membranes they influence cell volume via their osmotic force on cells. Abnormally raised osmolarity implies dysregulation in multiple organ systems, and cell dehydration as intracellular fluid moves to extracellular space to reduce the osmolarity, shrinking the cells (15). Community dwelling elders with serum osmolality ≥300mOsmol/L had a 40% increased risk of 8 year mortality (RR 1.4, 95% CI 1.0 to 1.9, multivariate adjustment), and greater risk of new disability over 4 years (RR 2.1, 95%CI 1.2 to 3.6, multivariate adjustment) compared to those with normal osmolality (16). Salt loss and isotonic dehydration are also important, but differ from water-loss dehydration, requiring distinct treatment (with isotonic fluids). Hyponatraemia is less common and less predictive of outcome than increased osmolarity in older people (associated with 25% increase in 5-year mortality (2)), so needs to be studied separately (6).

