- Serum osmolality information will be interpreted and provided to the care home manager (or deputy) and the resident's general practitioner
- Blood samples will be destroyed after analysis within the laboratory

Index tests (to use as described in original papers in systematic review):

The flow of the tests and questions will be roughly as follows (but we will adapt this to improve the way that the testing works as necessary). Before we interview and test a participant we will make sure that they have had a drink in the last half hour (making them an appropriate drink if not) and we will help them to the toilet (to empty their bladder) on the way to the interview:

- 1. Start by moving to an appropriate location, ideally the resident's own bedroom, and ensuring that if they would like a care worker or family member with them that this has been organised (and that if they do not want anyone with them this is also ensured).
- 2. On the way to the participant's room measure height and weight (in care homes chair scales)
 - Resident is settled in a comfortable seat. During this time to have a general friendly chat as appropriate with the participant. Once settled to ask short questions about how the resident is currently feeling (tired, thirsty, out of sorts, has a headache e.g. do you have a headache at the moment?)
 - EuroQoL-5D-3L assessment of quality of life (using EuroQol 5D, simple and fast, permission granted for us to use this free of charge, see http://www.euroqol.org/home.html)
- 3. Take blood samples (once resident has been sitting for 5- 10 minutes to ensure standardisation) as above. Label and store all samples, dispose of all sharps as per SOP.
- 4. Assessment of resident's mouth (timed to ensure the resident has not had a drink for 30 minutes at least)
 - Assess mouth for dry or furrowed tongue, dry inside cheek, dry or cracked lips
 - Ask short questions about favourite drinks, whether the participant ever misses drinks at any meal, ever misses drinks between meals, are they looking forward to their next meal, do they ever feel thirsty?
 - Measure body temperature (using an ear device)
 - Assess foot vein filling and finger capillary refill (base of middle finger, dominant side) times
 - Check for dry skin on calf, cheeks, inner arm, and check for presence of tears in eyes.
- 5. Once participant has been sitting comfortably for at 5-10 minutes check for orthostatic hypotension:
 - Assess pulse rate and blood pressure while still lying down.

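### Residents are given a drink within the half hour before testing: this pulls against the 30-minute drink-free rule for the mouth check and leaves current thirst and urine measured after an unstandardised, unrecorded drink

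*Protocol*

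**What the plan says.** The introduction to the index-test list (Protocol, Methodology) states: "Before we interview and test a participant we will make sure that they have had a drink in the last half hour", with researchers "making them an appropriate drink if not". It adds that "we will help them to the toilet (to empty their bladder) on the way to the interview".

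The list then runs, on the points that matter here:

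- Step 2: "Once settled to ask short questions about how the resident is currently feeling (tired, thirsty, out of sorts, has a headache". No interval since the drink is given.
- Step 3: blood is taken after 5 to 10 minutes of sitting. The Recruitment section (Visit 3) likewise puts it 5 to 10 minutes into the interview.
- Step 4: the mouth is examined, "timed to ensure the resident has not had a drink for 30 minutes at least".
- Step 7: a urine sample is collected near the end and tested for colour and specific gravity. No interval since the drink is given.

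The order is not rigid: "The flow of the tests and questions will be roughly as follows (but we will adapt this to improve the way that the testing works". On the reference standard, the Background says of serum osmolality that its "disadvantages include slow response to dehydration and rehydration".

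**The concern.** The drink acts on what some index tests measure, and it comes just before they are measured. Three features make this matter.

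- **Unequal effect.** The reference standard is chosen in the knowledge that it moves slowly. Current thirst and freshly formed urine may move faster. A dehydrated resident could then test negative on the sign while remaining positive on osmolality, which lowers apparent sensitivity.
- **Selective application.** The study drink is made only for residents who have not drunk recently. The Background lists missing drinks between meals among the promising signs of dehydration, so these residents may well include more of those with the target condition.
- **No record.** The Methodology data lists include no time or amount for this drink, and its volume and type are not fixed. The food-frequency questions cover habitual intake, and the step 8 observations concern drinks offered during the day. Neither would allow the analysis to examine the effect.

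The signs are measured once, at baseline, and feed both the single-sign accuracy estimates and the primary decision tree.

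**Working it through.** **1. The plan's own figures.** The only design figure is the precision of kappa. At 40% prevalence in both margins, chance agreement is 0.4² + 0.6² = 0.52.

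- Kappa 0.75: observed agreement = 0.52 + 0.75 × 0.48 = 0.88; SE = √(0.88 × 0.12 / 180) / 0.48 = 0.0505.
- Kappa 0.60: observed agreement = 0.808; SE = √(0.808 × 0.192 / 180) / 0.48 = 0.0612.
- Recruitment: 180 / 0.9 = 200.

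These match the stated 0.05, 0.06 and 200 to the precision given. Nothing below changes them.

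**2. The two timing rules.** Let d be the minutes from drink to interview start (0 to 30, from the drink rule) and m the minutes from interview start to the mouth check. The gap at the mouth check is d + m, and step 4 needs d + m ≥ 30. The protocol does not state m. Because blood is taken at 5 to 10 minutes and the mouth comes next, 10 to 20 is assumed, with 30 shown for comparison.

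| m (assumed) | Gap over d = 0 to 30 | Rule met in listed order if | Extra delay for a drink at d = 0 |
|---|---|---|---|
| 10 | 10 to 40 min | d ≥ 20 | 20 min |
| 15 | 15 to 45 min | d ≥ 15 | 15 min |
| 20 | 20 to 50 min | d ≥ 10 | 10 min |
| 30 | 30 to 60 min | always | none |

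A resident who drank 20 to 30 minutes beforehand satisfies both rules. One handed a drink at the start does not, unless step 4 is delayed or moved.

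**3. Thirst and urine.** Current thirst is asked before the blood sample, so it falls from 0 to about 40 minutes after the drink (d of 0 to 30, plus up to about 10), with no minimum. The pre-interview void is not listed as a sample, so the urine tested at step 7 has formed since that void, at about the time of the drink or after it.

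**4. The reference standard.** As an upper bound, suppose volume V of water is fully absorbed into total body water W (assumed: V = 0.15 to 0.30 L, W = 25 to 40 L). At the 295 mOsm/kg cut-off the fall is 295 − 295 × W / (W + V):

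- V = 0.15, W = 40: 1.1 mOsm/kg.
- V = 0.30, W = 25: 3.5 mOsm/kg.

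Less would be absorbed by the time blood is drawn. The effect is small, but not nil.

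**5. Direction of bias, with assumed values only.** Take a sign with sensitivity 0.70 and specificity 0.80 at 40% prevalence, and let the drink reverse a share r of positives in both groups. Sensitivity becomes 0.70(1 − r) and the false-positive rate 0.20(1 − r).

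| r | Sensitivity | Specificity | LR+ | LR− | Kappa |
|---|---|---|---|---|---|
| 0 | 0.70 | 0.80 | 3.5 | 0.30/0.80 = 0.38 | 0.24/0.48 = 0.50 |
| 0.10 | 0.63 | 0.82 | 3.5 | 0.37/0.82 = 0.45 | 0.216/0.472 = 0.46 |
| 0.25 | 0.525 | 0.85 | 3.5 | 0.475/0.85 = 0.56 | 0.18/0.46 = 0.39 |

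Under equal reversal the loss is in the ability to rule dehydration out; LR+ does not move. The documents give no value for r.

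**The case against.** The best defence is that the authors plainly had the interval in mind. The drink rule is tied to the start of the interview and the 30-minute rule to the mouth examination. The order is declared adaptable, so temperature, capillary refill, blood pressure, the cognitive test and the questionnaires could come before the mouth check without any idle wait. The toilet visit, weighing, settling and the quality-of-life questions also take time, so the assumed 10 to 20 minutes may be short. Each test has a standard operating procedure that is not shown here, and a pilot home exists so that such details can be changed.

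Much of this stands, and it rules out several stronger readings that a reader might infer:

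- *The two rules contradict each other.* They do not. They are in tension, and only the listed order after a fresh drink breaks the second.
- *Mouth and tongue signs are corrupted.* If the 30-minute rule is obeyed, they are protected from immediate wetting. They are at risk only where it is not.
- *The reference standard is untouched.* The Background says its response is slow, not absent.
- *A sign would lose its promising status.* The Background's criterion is LR+ above 2 **or** LR− below 0.5. With sensitivity 0.60 and specificity 0.80, LR− is 0.40/0.80 = 0.50, which already fails the second limb, and LR+ is 3.0. Reversing a quarter of positives in both groups gives 0.45 and 0.85, and LR+ is still 3.0. The sign qualifies before and after.
- *The results cannot apply to carers because carers would not give a drink first.* The protocol does not fix how the finished tool will be administered.

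Thirst is named in the Study summary's list of markers but not among the signs that the Background reports as meeting the likelihood-ratio limits. Urine colour and specific gravity appear in both.

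The defence does not reach current thirst or urine. The 30-minute rule covers the mouth only, and nothing in the protocol standardises or records the drink.

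**Conclusion.** The point holds in a limited form. The drink rule and the mouth rule need reconciling, because the order as written is likely to bring residents given a fresh drink to the mouth check too early (by 10 to 20 minutes, if the check falls 10 to 20 minutes into the interview). Separately, and even with perfect adherence to the mouth rule, current thirst and urine colour and specific gravity are measured after an unstandardised, unrecorded drink that is given selectively, against a reference that responds slowly. The likely direction is lower apparent sensitivity for those signs. The size cannot be derived from the documents, and the illustrative values above rest wholly on assumption. The sample size and its stated precision are unaffected. The change is worth making because the signs are measured once, the missing drink data cannot be recovered later, and the correction costs almost nothing.

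**What to change.** 1. Reconcile the two timing rules in the index-test section by stating the interval between the last drink and each affected test.
2. Ask current thirst and examine the mouth before any study drink is offered. In the listed order the blood sample lies between these steps, so it too would precede the drink. Keep the 30-minute rule for residents who drank on their own beforehand, since reordering does nothing for them.
3. Record the time and amount of the last drink for every participant, so that it can be examined in the accuracy analyses. This matters most for the step 7 urine, which may still follow a drink.
4. Optionally, test the first void as well. This is a trade-off: that urine precedes any study drink but has an unknown accumulation time, whereas emptying the bladder first gives a defined collection window.

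Cost: the study drink is offered some minutes later, and one or two data fields are added. The single-home pilot is the natural place to try the revised order.

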Effective osmolality is a function of sodium, potassium and glucose, and either serum sodium or glucose levels will be raised in water loss dehydration. Current dehydration (serum osmolality >300 mOsmol/kg), which develops following impending dehydration (295-300 mOsmol/kg), can be a medical emergency and 17% of those admitted to hospital with a main diagnosis of dehydration die within 30 days (2). If we can diagnose impending dehydration and prevent current dehydration this may improve life for older people and reduce health costs. Impending dehydration may cause poor health in its own right, so diagnosis of impending dehydration may improve health and quality of life for older people, but this will not be clear until we can diagnose and address impending dehydration. For these reasons this research will focus on water-loss dehydration, with serum osmolality as reference standard

Dehydration prevalence in frail older people varies by setting, level of care required, social deprivation and how hydration status is assessed. 4% of the growing number of older people in the UK live in a care home or long-stay hospital (rising to 21% of those aged 85+) – this is an extremely frail population (17). In Norfolk care homes we found that on a single assessment 30%

of 56 residents living in six care homes were dehydrated (with a furrowed tongue) (18), while a Californian nursing home study found 31% dehydrated at some point over 6 months (19).

Dehydration is more common as we age as our thirst response (20) and total body water (TBW) both reduce (10;21), and medications and increased dependence on carers increase dehydration risk (7). Contributors to low fluid intakes include clinical (dysphagia, functional impairment, dementia, and pain), social (lack of attention to drink preferences, inability of residents to communicate with staff, and lack of social support) and institutional factors (untrained and unsupervised staff). Water-loss dehydration, like falls or anaemia where identified, needs to be investigated to assess its causes, before addressing underlying problems. Where reduced fluid intake or increased losses are indicated, suggested interventions to prevent or reverse dehydration in older adults living in care homes include education and involvement of care staff, use of social times, drinks carts and water jugs, encouraging relatives to drink with residents, monitoring urine colour, and supporting those with swallowing problems (3;7).

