This will be a cohort study (researchers will be blind to reference standard results when assessing index tests). The design of this research incorporates understanding gained from the current literature on dehydration (summarised above), advice from members of PPIRes, discussions and debates with research mentors and steering group, results from (and debates during development the protocol for) our current systematic review of diagnostic accuracy of clinical and physical signs of water-loss dehydration in older people (which includes many current researchers in dehydration within the author group (25)), advice from the NIHR interview panel (who will be funding this research) and our ethics committee, discussions with care home managers and staff during the process of recruiting homes interested in participating in this research.

We will carry out primary research to improve identification of dehydration in residential care, assessing the diagnostic accuracy of clinical or physical signs that appeared promising in the diagnostic systematic review (25). Serum osmolality will be the reference standard for water-loss dehydration (295-300mOsmol/kg impending, >300mOsmol/kg current dehydration). As serum osmolality is not commonly available in residential care, a simple decision tree of tests to be carried out day to day by older people or their carers would be desirable.

Sample size: we will recruit 200 participants. Using the Kappa statistic as a measure of diagnostic accuracy and assuming a dehydration prevalence (current or pending categorised together) of approximately 40%, a sample size of 180 would ensure a standard error of no more than 0.05 for Kappa values in excess of 0.75. 200 participants recruited would allow for 10% to

terminate assessment before all signs are assessed or to provide unreadable blood samples. For values of at least 0.6, the standard error would be no more than 0.06. Thus, this sample size should provide an estimate of diagnostic accuracy with a precision to allow an assessment of the practical utility of the identified signs. Our previous experience of approaching 6 care homes with 213 residents recruited 50 participants to provide blood samples. Our potential set of participants for this study will be smaller as we will exclude those with diagnosed heart failure or renal failure, suggesting that approaching ~50 care homes will provide enough participants.

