Inclusion criteria: People aged 65+ living in residential care (care homes, nursing homes and mixed homes) in Norfolk (or on the Norfolk lists, this includes a few homes situated near the border in Suffolk). Inclusion of care homes will not be based on the star rating system (formerly conducted by the Care Quality Commission or CQC) as the rating system ceased in mid 2010.

We will include participants regardless of their capacity to provide informed consent, although the study is designed to protect all participants and include them only if they find the research acceptable. Inclusion of those with dementia was strongly encouraged by the NIHR interview panel that awarded the funding for this research, as those with dementia are at greatly increased risk of dehydration, so it is vital that the tool developed is applicable to those with dementia as well as those without. This decision has been strongly supported by care home managers and staff in my recent discussions with them over their involvement in this study. We will only include adults who can provide their own informed and signed consent OR whose consultee has provided signed consent that they believe that the resident would have consented if they were able to make the decision themselves.

We do not plan to stratify inclusion by age group (as most of those living in residential care will be either physically or mentally frail, all will be at some increased risk of dehydration), or by gender (although the samples are likely to be weighted towards women, as more care home residents are women). While we are aiming for a representative sample of care home residents, we will not exclude any interested participants on this basis.

Exclusion criteria: we will exclude those who the care home manager is aware has been diagnosed with renal failure or heart failure, as fluid physiology changes with these conditions (and fluid retention is more likely). Those in receipt of palliative care, or with illnesses that suggest they are unlikely to survive for at least 3 months will not be recruited. Additionally we will not seek to recruit people who are unable to provide their own consent, and are known to be frightened of, or upset by, needles or blood tests as we will assume that the process of the interview and blood sample will be upsetting to them.

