 - Help resident to stand in front of stable chair (using usual aids, help support them in case of dizziness), then measure BP after standing for 30 seconds and 3 minutes. After the 30 second measure ask if they feel dizzy (help them to a sitting position of any problems)
 - While standing assess whether breathing is normal, deep or deep and rapid
- 6. After the OH assessment :
 - Visual (Snellen) test
 - Mini-mental state exam (MMSE (31;32))

11

- Brief questions on sleep and continence (do you sleep well? How many hours do you sleep each night? Do you go to the toilet in the night? Do you feel tired when you get up in the morning? Do you ever worry you won't be able to reach the toilet to pass urine in time? Ever drink less in the evening so won't need to get up in the night?
- Brief questions on exercise (have you been outside in the past week? do you ever walk around with no clear purpose? Note use of walking aids within care home)
- Hospital Anxiety and Depression Scale (HADS) questionnaire (questions asked verbally)
- Short series of questions (in food frequency format) on assessment of intake of water, hot drinks, cold drinks and alcoholic drinks (short FFQ based on Nurses' Health Study (30))
- Establish ethnicity
- 7. Help participant to toilet (if help is needed), ask for a urine sample (collected in disposable "hat" in toilet). Help participant back to their preferred location in the home, make them comfortable with a drink and snack (where appropriate). Return to test urine:
 - Urine colour (against standard chart) and volume
 - Urine specific gravity (using dipstix), other dipstix measures
 - Urine specific gravity using refractometer
 - Urine volume (mls)
 - Weight of continence pad (used and dry)
- 8. Observation of resident during day (appropriate times for this will be planned, plus we will record any ad hoc observations following informed consent)
 - Length of wait when ask for help to go to toilet (if help needed)
 - Social interaction around drinking between meals (with carer, with visitor, with other resident(s), none)
 - Response to resident when offered a drink (express preference or not, drink immediately/drink over time/not tasted, any of drink left after 30 minutes)

To ask of care home manager for each participating resident:

- History of recent (over past week) vomiting, diarrhoea, cold, urinary tract infection (UTI) and/or fever

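### Breathing is rated only during the standing test, so residents who cannot stand have no score for this sign and its accuracy is estimated only in those who can

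*Protocol*

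**What the plan says.** The sequence of index tests is in the Methodology section of the Protocol. Step 5 is the orthostatic hypotension check. The instruction is "Help resident to stand in front of stable chair (using usual aids, help support them in case of dizziness", with blood pressure taken at 30 seconds and at 3 minutes. If the resident is dizzy after the first reading, the researchers are to "help them to a sitting position of any problems". The breathing item follows within the same step: "While standing assess whether breathing is normal, deep or deep and rapid". Breathing is rated nowhere else in the sequence.

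Three other parts of the Protocol bear on this:

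- **Population (Study design, inclusion and exclusion criteria).** Care homes, nursing homes and mixed homes are all eligible. Inability to stand is not an exclusion. Age stratification is declined "as most of those living in residential care will be either physically or mentally frail". The Background adds that "medications and increased dependence on carers increase dehydration risk".
- **Status of the test sequence.** The list is headed "Index tests (to use as described in original papers in systematic review". The order is described as rough, "but we will adapt this to improve the way that the testing works as necessary".
- **Sample size.** 200 residents are recruited to give 180 evaluable. The 10% margin is for residents who "terminate assessment before all signs are assessed or to provide unreadable blood samples".

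**The concern.** A postural change in blood pressure cannot be measured without standing. Breathing can be observed in a chair, and the resident is already settled in a seat from step 2 until the postural test. A resting observation is therefore available for everyone interviewed, but none is recorded.

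The missing scores would not fall at random. They fall on residents who cannot stand, who are likely to be among the more dependent, and the Background names dependence on carers as raising the risk of dehydration. Two things are at stake:

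- Secondary aim 1 promises the accuracy of each sign in frail residents. For breathing, the estimate would describe only those able to stand.
- The tool is meant for day-to-day use in residential care. A branch that splits on breathing while standing could not be followed for a resident who cannot stand.

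**Working it through.** **1. What follows from the text.** Breathing is rated while standing, there is no other rating, residents who cannot stand are eligible, and no alternative posture or code is given. Taken together, a resident who cannot stand has no breathing score. The text does not say this in so many words. It is what happens if the sequence is followed as written.

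**2. The plan's own precision figure.** Inputs from the sample size paragraph: prevalence 40%, n = 180, kappa 0.75 and 0.6. Taking both marginals as 0.40:

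- Chance agreement: pe = 0.40² + 0.60² = 0.52.
- Observed agreement: po = kappa × (1 − pe) + pe, which is 0.88 at kappa 0.75 and 0.808 at kappa 0.6.
- SE = √[po(1 − po)/n] / (1 − pe).
- Kappa 0.75: √(0.88 × 0.12/180)/0.48 = 0.0505.
- Kappa 0.6: √(0.808 × 0.192/180)/0.48 = 0.0612.

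These agree with the stated 0.05 and 0.06 to two decimals, and 180/(1 − 0.10) = 200 as stated. The sample size is not in dispute.

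**3. Loss of precision for this sign.** Let f be the share of the 180 evaluable residents with no breathing score. The Protocol gives no value; 10% to 40% is an assumption. Ratings lost = 180f, and the SE is multiplied by 1/√(1 − f).

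| f (assumed) | Lost | Rated | SE multiplier | SE at kappa 0.75 |
|---|---|---|---|---|
| 0 | 0 | 180 | 1.00 | 0.050 |
| 10% | 18 | 162 | 1.05 | 0.053 |
| 20% | 36 | 144 | 1.12 | 0.056 |
| 30% | 54 | 126 | 1.20 | 0.060 |
| 40% | 72 | 108 | 1.29 | 0.065 |

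If some residents who cannot stand are already among the 20 whom the plan allows to be lost, f is smaller than the share unable to stand.

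**4. Is accuracy biased?** Let s₁ and s₂ be the sensitivity of the sign in dehydrated residents who can and cannot stand, and let f now be the share of dehydrated residents who are unrated. The estimate from rated residents minus the value for all residents is s₁ − [(1 − f)s₁ + f s₂] = f(s₁ − s₂). All inputs here are assumed:

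- s₁ = s₂: bias 0 at any f.
- f = 20%: 0.5 against 0.6 gives −0.02; 0.5 against 0.4 gives +0.02.
- f = 40%: the same pairs give −0.04 and +0.04.

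The same algebra applies to specificity. A higher prevalence of dehydration among residents who cannot stand does not by itself move either measure. The document fixes neither the presence nor the direction of bias.

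**The case against.** The strongest reply is that this is operating detail. The flow is declared adaptable, Quality assurance puts test delivery into standard operating procedures with reproducibility checks, and one home is used as a pilot so that changes can be carried forward. Part of this stands: the Protocol never says that these residents go unrated. But none of these provisions sets a posture for breathing. Adapting case by case would mix seated and standing ratings in one variable, which works against the standardisation sought under Quality assurance. An analysis plan can set rules for missing index tests, but it cannot recover an observation that was never made.

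A second reply is that standing may be deliberate, since index tests follow their source papers. Those sources cannot be seen here, so this stands as a reason not to replace the standing rating. It is no reason against adding a resting one.

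A reader might also infer that frail residents are rated under exertion, so that the manoeuvre itself creates false positives. The Protocol does not support this. Residents stand with their usual aids and with physical support (step 5 and Safety considerations), and nothing in the text says that standing changes the breathing category. Everyone rated is rated in the same posture, so the study measures breathing while standing. An illustration can be built: take resting sensitivity 0.40 and specificity 0.90, and let a share x of otherwise normal breathers turn positive on standing. Then LR+ = (0.40 + 0.60x)/(0.10 + 0.90x), which is 4.0 at x = 0, 2.4 at 10% and 1.9 at 20%, and falls below 2 only above x = 0.2/1.2, about 17%. Every input is assumed. The LR+ above 2 in the Background describes signs found in the systematic review; it is not this study's rule for selecting signs.

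**Conclusion.** The point holds as a gap in data collection for one sign. As written, breathing is unrated in residents who cannot stand, its accuracy is estimated only in those who can, and a tree using it would not reach the others. Precision for this sign falls with the share unrated: standard errors rise by about 5% to 29% if that share is 10% to 40%, a range that is assumed because the Protocol gives no figure.

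It would be tempting to conclude that the sign's accuracy is biased. That goes beyond the document: bias needs the sign to perform differently in residents who cannot stand, and its size and direction are unknown.

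The impact is small. Breathing is one of many candidate signs and is not among the promising ones named in the Study summary or the Background. CART was chosen partly so that not every sign need be assessed in every person. The primary aim is not threatened.

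**What to change.** In step 5, add a breathing rating in the same three categories, taken at rest before the resident stands, for every resident interviewed. Keep the standing rating as a separate item, so that the two postures are never mixed in one variable and any definition taken from a source paper is preserved. Report the number rated in each posture and the number not rated.

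Name the resting posture when making the edit: step 5 speaks of the resident sitting comfortably and then of readings taken while still lying down, and these two statements need to be reconciled.

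The cost is one line in the test sequence and its operating procedure, and one extra field on the data form. It needs no equipment and adds no appreciable time or burden for the resident.
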